Substance abuse costs our nation over \$600 billion annually. Drug addiction treatment reduces drug use and has been shown to reduce the health and societal cost far more than the actual cost of the treatment. Treatment is also much less expensive than other options. Outcomes of drug treatment programs are dependent on adequate treatment length and drop out is one of the major problems in the current treatment program. It is therefore critical to optimize drug dosing regimens in patients to improve adherence and success of the treatment programs. In 2012, an estimated 400,000 adults aged 18 or older were current illicit drug users. Many of these were pregnant women. In the most recent National Survey on Drug Use and Health (2012), 6% of pregnant women reported using illicit substances within the past 30 days¹. Azadi et al found that 3% of women were urine-positive for illicit opioids at the time of delivery². Currently, the standard of care for an opioid-dependent pregnant woman in most institutions is methadone, however buprenorphine (BUP) is also used for this indication as it is FDA-approved for opioid addiction although not specifically for pregnant women. There has been increasing evidence that BUP may have comparable efficacy to methadone, and may have fewer severe neonatal complications especially neonatal abstinence syndrome (NAS). In a recent study, BUP-exposed, as opposed to methadone exposed, neonates required significantly less morphine for treatment of NAS, had significantly shorter duration of treatment for NAS and had significantly shorter hospital stays³. Methadone, a full μ agonist, has significant adverse reactions such as Q-T prolongation, potential for life-threatening respiratory depression and extreme sedation⁴⁻⁶. Conversion from illicit narcotic use to methadone commonly requires hospitalization for 3-4 days as the dose of methadone is titrated upward based on the patient's symptomatology^{4,5}. Upon hospital discharge methadone treated patients receive daily dosing of medication at outpatient clinics that monitor the patients for continued illicit drug use. This requirement is extremely burdensome on the patients since many do not have transportation and they must arrive at the clinics in the morning. BUP, a partial μ agonist, has decreased severity of adverse reactions and therefore physicians are able to convert patients on an outpatient basis. The patient is given a 1-4 week supply of oral medication thus eliminating the burdensome task of attending daily clinics for drug administration. These benefits of BUP are changing the management of drug addiction dramatically and more institutions will turn from in-patient treatment with methadone to the outpatient strategy with BUP. The American College of Obstetricians and Gynecologists in its 2012 Committee Opinion indicates that the literature "supports the use of buprenorphine as first line treatment for pregnant opioid –dependent women"⁷. Similarly the American Society of Addiction Medicine supports the use of buprenorphine in opioid- addicted pregnant women⁸ and the World Health Organization (WHO) which encourages availability of a buprenorphine option has described the worldwide availability of buprenorphine⁹. The dosing of BUP currently is based on studies in men and non-pregnant women and limited animal data that related plasma concentrations of BUP to the degree of saturation of the μ receptor in the brain¹⁰⁻¹³. These studies suggest that a dose of 16 mg daily saturates 95% of the μ receptors. The plasma half-life in non-pregnant subjects is approximately 22 hours and therefore a dose of 16 mg/day appears to be sufficient to saturate the receptors. The standard recommended dosing regimen for sublingual BUP is therefore 8 mg bid or 16 mg QD. Unlike for methadone, where increased dosing is recommended during pregnancy, currently there are no guidelines on dosing BUP in pregnant women. The dosing regimen used in non-pregnant subjects does not appear to be adequate for pregnant women. Dosing is adjusted to the patient's symptomatology using the Clinical Opiate Withdrawal (COW) score, some of which is subjective and some based on objective physiological parameters. The failure rate for BUP is highest (33%) during the induction period i.e. the time from stopping illicit drug use to the point of achieving a stable dose of BUP³. This suggests that the current treatment regimens for BUP are inadequate for many women. Indeed at Magee-Womens Hospital, using COW scores to determine a dosing regimen has resulted in many women requiring doses higher than the 16 mg daily dose used in non-pregnant subjects. The high failure rate of BUP during induction and the experience at Magee are

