We will enroll eligible, consenting pregnant women who are receiving sublingual BUP (subutex) in a supervised hospital or outpatient clinical setting because of their opiate addiction. Due to the possibility of limited subject availability at individual centers, recruitment can target subjects receiving pregnancy care at other institutions. Likewise, since buprenorphine is commonly not dispensed in a hospital setting, subjects may need to be recruited from clinics where buprenorphine is provided to pregnant women as part of a structured maintenance program. To facilitate enrollment, recruitment can target one or more specific aims as summarized below.

For Specific Aims 1 and 3:

We will recruit 40 eligible, consenting pregnant women to an 'extensive sampling' pharmacokinetic (PK) study in which they will be studied three times: once between 8 0/7-20 6/7, once between 21 0/7-35 6/7 and once at 4-6 weeks post-delivery. Studies done during pregnancy should be at least 12 weeks apart. We will also obtain patient demographics and medical history.

We will encourage subjects to complete as many PK studies as possible; however, subjects are only required to complete one PK study in order to participate in this portion of the study. Each study is 13 hours in length for BID dosing, 9 hours for TID dosing, 7 hours for QID dosing, and 6 hours for five times daily dosing.

Each PK study will be performed after the subject has been on a stable dose of BUP for a minimum of 7 days. Physiologic testing (pupillometry, galvanic skin response, and heart rate), COW and craving scores will be performed before the daily dose of BUP is taken.

Measurement Type	Dosing	Length of Study	No. of Measurements
Blood (BUP/metabolite)	BID	13 hrs	Baseline + 12 additional
Physiologic			Baseline + 9 additional
Blood (BUP/metabolite)	TID	9 hrs	Baseline + 12 additional
Physiologic			Baseline + 9 additional
Blood (BUP/metabolite)	QID	7 hrs	Baseline + 10 additional
Physiologic			Baseline + 7 additional
Blood (BUP/metabolite)	5 times/daily	6 hrs	Baseline + 10 additional
Physiologic			Baseline + 7 additional

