The following collection and processing instructions apply to all blood and saliva samples collected during this study. The samples collected will be dependent on which parts of the study the subject participates in.

Blood samples will be collected as follows:

- Maternal and Cord Blood Samples for BUP Analysis: One 10 mL heparinized vacutainer tube will be drawn at the time points described in sections D.5.vi and D.5.ix. The tube should be centrifuged at 1500 g at 4°C for 15 minutes. Plasma samples will then be transferred into polypropylene tubes and frozen at -80 degrees centigrade until analysis.
- PBMC analysis: One 5 mL EDTA vacutainer tube will be drawn with the first sample (pre-dose) at each PK study visit and at delivery (applicable to all subjects), when possible. The sample should be stored at room temperature. Notify [name] lab in advance at [contact] / [contact] or via email ([contact]) to allow for pick up and processing within 4 hours of collection.
- DNA Analysis: One 10 mL EDTA vacutainer tube will be drawn at the Baseline Screening Visit. If the DNA sample is unable to be obtained at the screening visit, it may be collected anytime during the study when blood is being drawn. The sample should be frozen at -80 degrees centigrade until analysis.

Saliva samples will be collected using a Sarstedt Salivette collection device. The salivary collection sponge can be centrifuged later in the day. Salivary pH will be determined. Oral fluid samples will then be transferred into polypropylene tubes and frozen at -80 degrees centigrade until analysis.

D.5.xii. Study Outcome Measures and Ascertainment (Applicable to all Subjects):

Mothers and infants will be followed until they are discharged from the hospital, at which time relevant data from the labor, delivery and nursery records will be recorded.

a. Primary Outcome:

The primary outcome is the exposure to BUP (AUC) during pregnancy and the post-partum state.

b. Secondary Outcomes Maternal:

Other maternal outcomes to be measured are:

1. The relationship between COW and Craving scores, pupillometry, heart rate, blood pressure

and GSR scores to the maternal plasma concentration of BUP and its major metabolites

2. The impact of polymorphisms of CYP 450 and conjugating enzymes of buprenorphine on plasma concentration of BUP and its major metabolites
3. The relationship between the umbilical cord and maternal concentration of BUP and its major metabolites

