4. The relationship between maternal dose and concentration of buprenorphine and metabolites in umbilical cord, maternal and infant hair
5. The relationship between maternal plasma and breast milk concentrations of BUP and major metabolites
6. Cumulative amount of BUP and its metabolites excreted in breast milk.

c. Secondary Outcomes Neonatal:

Neonatal outcomes to be measured include the following:

1. Relationship between concentrations of BUP and its metabolites in maternal and umbilical cord plasma and maternal and newborn hair and maternal dose and parameters of neonatal withdrawal
2. Infant hospital days
3. Birthweight
4. Gestational age
5. Neonatal Complications including: Respiratory distress syndrome (RDS), stillbirth, neonatal death, intraventricular hemorrhage as determined by cranial ultrasound, bronchopulmonary dysplasia, necrotizing enterocolitis, early onset of neonatal sepsis, seizures, retinopathy of prematurity (ROP), and hyperbilirubinemia.

D.5.xiii. Statistical Considerations

Data Analysis Plan:

The primary outcomes will be the area under the plasma concentration x time curve (AUC) of BUP during early pregnancy compared to the AUC in late pregnancy. We will also compare the AUC of BUP and metabolites during early and late pregnancy and the post-partum period. Mixed-effect models, repeated measures ANOVA or paired t-testing, will be used to compare early to late-pregnancy and overall pregnancy values to the postpartum values. Secondary outcomes such as metabolite concentrations will be analyzed in the same fashion. Additional analysis will also include multiple regressions to evaluate the relationships between maternal and fetal plasma concentrations of BUP and its metabolites, placental p-glycoprotein, physiologic parameters and CYP3A4/5 expression. We will also use population pharmacokinetic analysis to evaluate the contribution of various covariates (i.e. maternal genotype, BMI, etc.) to the observed variability in the trough plasma concentrations of BUP.

Primary Hypothesis

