Based on data from our recently completed study, the dose-adjusted AUC was 2.34 ± 1.82 (ng/ml).hr in pregnant women at a mean gestational age of 34 weeks. In postpartum women, the dose adjusted AUC was nearly 100% higher at 4.0 ± 2.8 (ng/ml).hr. We anticipate that the AUC in the first half of pregnancy will be somewhere between values of non-pregnant women and those of pregnant women in the latter part of pregnancy. The sample size required to demonstrate a 50% difference between the dose adjusted AUC in the first half of pregnancy and the second half of pregnancy as well as a 50% difference between the dose adjusted AUC in the first half of pregnancy and the postpartum state is 37 ($\alpha = 0.05$, $\beta = 0.80$). We will recruit an additional 3 subjects to

account for dropouts or noncompliance. The secondary physiological outcomes will also be addressable with this sample size as the variance in pupil measurements is small (4.65 ± 0.4 mm at baseline and 2.64 ± 0.08 mm at 2 hours in the paper of Middleton et al¹³) and each patient will provide data from 2-3 PK studies. Thus there will be 120 studies that relate a physiologic variable to plasma buprenorphine. Specific Aim 5 which relates NAS to various parameters (maternal dose, maternal and cord plasma buprenorphine /metabolite concentrations etc.) can be addressed with the projected sample size as correlations between the dependent variable NAS and the numerous independent variables i.e. maternal dose, maternal concentration at delivery, maternal hair concentration, cord blood concentration, newborn hair concentration etc. can be performed with samples size of 15. We assume that 50 % of these infants will have some degree of NAS so the sample size of 40 should be sufficient. If the prevalence of NAS is lower, we can recruit additional subjects. Since the extensive PK studies will not be required to test this hypothesis, recruitment should be easier and can be done at secondary sites if needed.

Secondary Hypotheses

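### Neither the pupil spread in a cited paper nor the count of 120 studies supports the unqualified claim that the physiologic outcomes are addressable with this sample size

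*Combined protocol and SAP*

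**What the plan says.** The sample size of 37, plus 3 for dropout, is derived in D.5.xiii (Primary Hypothesis) for comparisons of dose-adjusted AUC. The same paragraph extends it to the physiologic measures: "The secondary physiological outcomes will also be addressable with this sample size as the variance in pupil measurements is small". The evidence is a cited paper reporting "4.65 ± 0.4 mm at baseline and 2.64 ± 0.08 mm at 2 hours". The sentence then gives a second reason, that "each patient will provide data from 2-3 PK studies", and concludes: "Thus there will be 120 studies that relate a physiologic variable to plasma buprenorphine".

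The outcome this is meant to cover is in D.5.xii, maternal secondary outcome 1: "The relationship between COW and Craving scores, pupillometry, heart rate, blood pressure" and galvanic skin response (GSR), each in relation to maternal plasma buprenorphine (BUP) and its major metabolites.

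Three other places bear on the claim:

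- D.1 says that "subjects are only required to complete one PK study in order to participate in this portion of the study". D.4 (Part A), D.5.iii and D.5.iv repeat the one-visit minimum.
- D.3 introduces the secondary questions with a warning that the sample may be inadequate for some of them. Question 3 on that list is the pharmacodynamic one.
- The Data Analysis Plan in D.5.xiii says: "Additional analysis will also include multiple regressions to evaluate the relationships between maternal and fetal plasma concentrations of BUP". The list that follows includes the physiologic parameters. No term for woman or visit is mentioned.

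**The concern.** Whether a sample can address a relation between an effect measure and plasma concentration depends on the slope, the spread of concentration and the residual spread around the line. The plan gives none of these for any of the six measures. It gives a spread for pupil size only, at two fixed times.

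Aim 3 asks whether an objective measure can gauge plasma BUP. If the protocol says the sample is sufficient, a null result for GSR or heart rate may be read as evidence of no relation. In the other direction, counting visits as the unit of information and naming multiple regression with no term for woman leaves room for an analysis that treats repeated rows as independent. That would make confidence intervals too narrow.

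**Working it through.** **1. Where 37 comes from.** The inputs are in D.5.xiii: late-pregnancy AUC 2.34 ± 1.82, a 50% difference (0.5 × 2.34 = 1.17), α = 0.05 (two-sided assumed) and 80% power. The unpaired formula gives n = 2 × (1.960 + 0.842)² / (1.17/1.82)² = 38 per group, close to the stated 37. Another reading also fits: a paired t-test with SDs 1.82 and 2.8 and an assumed correlation of 0.5 has an SD of difference of √(1.82² + 2.8² − 2 × 0.5 × 1.82 × 2.8) = 2.46 and needs 37. The plan names no formula. On either reading 37 is driven by AUC alone, and no physiologic figure enters.

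**2. What the pupil figures support.** The change is 4.65 − 2.64 = 2.01 mm. If the ± values are SDs and the two times are uncorrelated, the SD of change is √(0.4² + 0.08²) = 0.408 mm and the standardized change is 2.01/0.408 = 4.93. A paired t-test then has 97% power with 3 women. With a correlation of 0.9 the SD of change is 0.330 and the standardized change 6.09, so 3 women still suffice. If the ± values are standard errors from an assumed 5 to 20 subjects, 4 to 9 women would be needed. On no reading do the figures lead to 37 or 40, and they do not concern a relation with concentration.

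**3. The count of studies.**

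| Visits per woman | Studies from 40 women |
|---|---|
| 3 (all complete) | 40 × 3 = 120 |
| 2 (lower end of 2-3) | 40 × 2 = 80 |
| 1 (required minimum) | 40 × 1 = 40 |

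The 120 also counts the 3 women added to cover dropout; without them the maximum is 37 × 3 = 111.

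**4. Sensitivity of a between-woman correlation (illustration).** The plan gives no target, so two-sided 0.05 and 80% power are carried over from the primary comparison. Detectable r = tanh(2.802/√(n − 3)):

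- n = 40 women: 0.43
- n = 37 women: 0.45
- 120 units, if they were independent: 0.25

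At a true r of 0.25, power = Φ(atanh(0.25) × √(n − 3) − 1.96), which is 34% for 40 and 79% for 120. The choice of unit therefore matters.

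**5. If repeated rows were treated as independent.** With m rows per woman, exchangeable within-woman correlations ρy (measure) and ρx (concentration) and no true relation, the variance of the estimate is inflated by about V = 1 + (m − 1)ρyρx. A nominal 5% test then rejects with probability 2Φ(−1.96/√V). The correlations are assumptions. Three visits with one value each give m = 3; three visits with ten values each (the twice- and three-times-daily schedules) give m = 30.

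| Rows per woman | ρx | ρy = 0.3 | ρy = 0.5 | ρy = 0.7 |
|---|---|---|---|---|
| 3 | equal to ρy | 7% | 11% | 16% |
| 3 | 0.1 | 6% | 6% | 7% |
| 30 | equal to ρy | 30% | 49% | 62% |
| 30 | 0.1 | 15% | 21% | 26% |

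Simulation under the same assumptions agrees to within about two percentage points.

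**The case against.** **The plan hedges.** D.3 warns that the sample may be inadequate for some secondary questions, section B calls the pupillometry and GSR work an exploration, and Aim 3 speaks of potential endpoints. This stands, and it tempers the risk that a null result is misread. It does not rescue the sentence in D.5.xiii, which drops the hedge and so contradicts D.3.

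**Pupil spread is not the only reason given.** True: the number of visits is the second. Step 3 shows that it is no firmer.

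**Mixed models are already named.** They are, as one of three options for comparing early pregnancy, late pregnancy and postpartum, with secondary outcomes such as metabolite concentrations treated likewise. The physiologic parameters are assigned to multiple regressions. A reader might infer that the plan intends to pool visits or time points as independent rows. It does not say so; it is silent on clustering. The rates in step 5 are what an avoidable choice would cost, not a property of the stated plan.

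**A reader might infer that 40 women are too few, or that only r of 0.43 or more can be detected.** The documents do not support that. The outcome is not defined as a between-woman correlation. D.5.vii schedules 8 to 10 physiologic measurements per visit, each at a blood-draw time in D.5.vi, so much of the information is within women. With one visit each, 10 points and independent errors, there are 400 − 40 = 360 within-woman degrees of freedom, and detectable r is about tanh(2.802/√357) = 0.15. Allowing assumed serial correlation up to 0.7 takes this to about 0.25. A common slope is assumed throughout.

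**Two further inferences also go too far.** One is that the cited paper's subjects or baseline conditions differ from those here. Section A cites it within a group about which it says "The dosing of BUP currently is based on studies in men and non-pregnant women and limited animal data", but that describes the group, and the paper's own conditions are not given. The other is that 0.08 mm at 2 hours means pupil size cannot rank women by plasma level. That needs the ± to be an SD, which is not stated, and uniform values at one time would not prevent pupil size from tracking concentration over time.

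**Conclusion.** The statement in D.5.xiii that the physiologic outcomes are addressable is unsupported and conflicts with D.3. The first reason concerns a pre/post change in one of six measures. The second gives a maximum (120) as the expected count when the plan's own terms allow 40 to 120, and it treats repeat visits as if they were separate units.

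This is a missing justification, not evidence that the sample is inadequate. The outcomes are secondary and the primary sample size is untouched. The practical gain lies in the analysis specification: a model with no term for woman could reject a true null about 6-16% of the time with one value per visit and 15-62% with ten, over the assumed within-woman correlations in step 5. The figure of 0.43 rests on assumed two-sided 0.05 and 80% power, and applies only to a between-woman correlation.

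**What to change.** 1. **D.5.xiii, Primary Hypothesis.** Delete the pupil-variance rationale and the sufficiency statement. Give 120 as a maximum (40 to 120 studies from up to 40 women). Describe the physiologic analyses as exploratory and reported with confidence intervals, in line with D.3.
2. **D.5.xiii, Data Analysis Plan.** For the physiologic parameters, replace the multiple regressions with a mixed model of each measure on plasma BUP at the same time point, with random effects for woman and for visit within woman. Report within-woman and between-woman relations separately.
3. **Any stated sensitivity.** Do not print r = 0.43 as the detectable effect for that model. If it is quoted, label it as a between-woman correlation with 40 women (0.45 with 37), two-sided 0.05 and 80% power assumed.

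The cost is protocol wording only. The physiologic times already fall on blood-draw times, so no patients, visits or measurements are added. The downside is that the stated sensitivity becomes less favourable and confidence intervals for between-woman relations widen.

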D.3. Secondary Research Questions

This study will also attempt to address the following questions recognizing that an inadequate sample size may be available for some of these outcomes:

1. How quickly do buprenorphine trough concentrations decrease after delivery?
2. What maternal covariates impact the plasma concentration of BUP and its metabolites?
3. Is there a pharmacodynamic parameter that reflects maternal satiety and withdrawal?
4. What is the relationship between maternal BUP and metabolite concentrations and cord blood concentrations and NAS risk?
5. What is the infant's exposure to BUP through breast milk?
6. How quickly in the postpartum period does BUP appear in breast milk?
7. How well does cotinine concentration relate to smoking reported by the subject on the smoking questionnaire?
8. Does smoking modify the relationship between physiologic measures and plasma buprenorphine concentrations?
9. Does smoking impact the risk of NAS?
10. How well do catecholamine concentrations reflect physiologic parameters and satiety?

D.4. Study Design

This will be a multicenter pharmacokinetic (PK) and pharmacodynamic (PD) study of sublingual BUP in pregnant women on the medication for their drug addiction. There are several parts to this study and subjects may participate in one or more parts, as described below.

For subjects that choose to participate in procedures other than the PK studies (Parts B-E), only minimal testing is required prior to coming to the hospital for delivery. Blood samples for BUP determination and DNA (deoxyribonucleic acid) analysis will be obtained at the time of consent.

Part A: Subjects will participate in PK studies that will occur at 2-3 different times during the study: 1) between 8 and 20 weeks of pregnancy; 2) between 21 and 35 weeks of pregnancy; and 3) between 4 to 6 weeks postpartum. There will be a minimum of 12 weeks between PK visits during pregnancy. Subjects must complete at least one PK visit in order to participate in this portion of the study.

Part B: Prior to delivery, we will collect maternal blood samples. At the time of delivery, we will collect a cord blood sample, a 3 x 3 cm placental sample, and a 3 inch umbilical cord sample.

Part C: Hair samples from the mother and baby collected within 3 days after delivery

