Part D: While the baby is hospitalized, we will request 1-3 samples (at least 1 ml but no more than 5 ml each) of the mother's breast milk for analysis of BUP. We will collect 2 infant heel stick samples with each breast milk collection. One heel stick sample will be collected prior to a breast feeding (trough level) and another one 1 hour after the feeding (peak level).

Alternatively, subjects may also elect to participate in Part D during 1-3 routine postpartum PRC appointments, as long as they are still taking Buprenorphine (Subutex or Suboxone). The research staff will work with the patient to coordinate the sample collection with the timing of the patient's last BUP dose.

During each visit, we will request an infant heel stick sample prior to a breast feeding (trough level). The subject will then collect a breast milk sample. We will reserve a sample of at least 1 ml but not more than 5 ml for analysis of BUP and return the remainder to the mother for her infant. We will then collect a second infant heel stick sample 1 hour after the feeding (peak level). Ideally, we will collect both breast milk and heel stick samples during each collection; however, it is acceptable to collect only breast milk samples if the mother does not consent to the collection of heel stick samples.

Part E: We will collect 1-2 maternal blood samples while the patient is in the hospital, at least 2 days apart. We will continue to collect maternal blood samples during the subject's routine visits to the MWH BUP clinic weekly for the next 4 weeks. The time of the blood draw, the time of the last dose administration, and the dosing history will also be recorded.

D.4.i. Entry criteria include:

1. Age between 18 – 45 years
2. Currently on a stable two, three, four, or five times daily dose of sublingual BUP. Subjects participating in Part D during postpartum PRC visits must be taking Subutex or Suboxone.
3. Gestational age < 19 6/7 weeks *
4. Singleton gestation
5. Able to give informed consent and undergo study procedures
6. Willing to have urine samples screened for the presence of alcohol, barbiturates, opiates, cocaine (or metabolites), benzodiazepines, synthetic opioids and PCP *
7. Willing to participate in at least one PK study either during pregnancy or in postpartum *

*Requirement applies only to those subjects in the PK study

D.4.ii. Exclusion Criteria include:

1. Major fetal anomalies or malformations
2. HIV or AIDS

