No attempt will be made to mandate clinical management of the subjects. If complications arise, the patient will still be eligible for additional PK studies unless the complication affects the pharmacology of BUP i.e. significant liver or renal disease.

If a patient who consented to any part of this study (Parts A-E) is dismissed from her Medication Assisted Treatment (MAT) clinic due to non-compliance, she will be dismissed from the study and another subject will be recruited to replace her.

If non-prescribed opiates/opioids are detected during any PK screening visits, the subject will be ineligible to complete the pending PK visit. Subjects may be re-screened at a later date as long as they are within the gestational window for the PK visit. If a subject in the PK study has two positive drug screens for non-prescribed opiates/opioids during any screening visits, she will be dismissed from the study and replaced with another study subject.

At the time of enrollment, patients will consent to those components of the study that they wish to participate in. Subjects are required to complete at least one PK study in order to participate in this portion of the study. If a subject consents to portion of the study and they are unable to complete it within the acceptable timeline, they will still be eligible to participate in the remaining

parts of the study they consented to.

D.5.iv. Study PK Visits:

Once the subject has signed the consent form, completed the Screening Visit, and is deemed eligible for the study, the research staff will establish a schedule for the subject to undergo their first PK study. Subjects participating in the PK study must complete at least one PK study.

Screening Visits will be conducted within 1-2 weeks prior to each PK study and subjects must continue to meet the criteria listed in section D.4, with the exception of exclusion criteria items 6 and 7. A urine drug screen (Immunoassay) will be performed on the day of the PK study.

Each PK study, both during and after pregnancy, will be performed after the subject has been on a consistent two, three, four, or five time daily dose of BUP for a minimum of 7 days.

D.5.v. BUP Administration During PK Visit:

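### The 120 PK studies behind the physiologic outcomes are a ceiling stated as the expected total, and the plan does not say which visits a woman must complete to count toward the 37

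*Combined protocol and SAP*

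**What the plan says.** **Count of studies.** The Primary Hypothesis text of D.5.xiii says the physiologic outcomes can be addressed with the planned sample. It cites the small variance of pupil measurements and then states that "each patient will provide data from 2-3 PK studies. Thus there will be 120 studies that relate a physiologic variable to plasma buprenorphine".

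**Visits per woman.** D.1 describes 40 women recruited to an extensive-sampling study "in which they will be studied three times", but adds that "subjects are only required to complete one PK study in order to participate in this portion of the study". D.4, Part A, speaks of two to three occasions and then says "Subjects must complete at least one PK visit in order to participate in this portion of the study". The entry criteria (D.4.i) ask a PK subject to be "Willing to participate in at least one PK study either during pregnancy or in postpartum". Their limit of "Gestational age < 19 6/7 weeks" brings women in while the early window is still open.

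**Missed visits.** Under D.5.iii, after a screen positive for non-prescribed opioids "the subject will be ineligible to complete the pending PK visit", with re-screening possible inside the window. Of women who consent to a part and miss it, the section says that if "they are unable to complete it within the acceptable timeline, they will still be eligible" for the remaining parts. Replacement is stated for women dismissed by their treatment clinic or after two positive screens. None is stated for a missed window.

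**Sample size and analysis.** D.5.xiii gives 37 for a 50% difference in dose-adjusted AUC in two contrasts, early versus late pregnancy and early pregnancy versus postpartum, and adds three subjects for dropout. The Data Analysis Plan lists mixed-effect models, repeated measures ANOVA or paired t-tests. The Secondary Hypotheses text names a paired t-test for pregnancy versus postpartum and includes AUC among the parameters compared.

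**The concern.** The total of 120 is introduced as a consequence of two to three studies per patient, and it is not one. It needs perfect attendance by all 40 women, while the same paragraph expects to lose three and other sections ask for one visit only. A reader judging whether the physiologic analyses are adequately supported is given the best case as the forecast. The studies are also repeated measurements on the same women, so even 120 would not be 120 independent observations.

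The primary question has a related gap. A woman with a single visit, even one made only postpartum, can occupy one of the 40 places and add no within-woman pair. If the 37 means women with both windows of a contrast, no rule ensures that this number is reached, and nothing in the plan would show at the close of recruitment whether it was. The choice of test then matters. A paired t-test drops single-visit women from the AUC comparison, whereas a mixed model can keep them.

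**Working it through.** **1. The plan's 120.** Inputs: 40 women (D.1), 2–3 studies each and 3 dropouts (D.5.xiii), minimum of 1 study (D.1, D.4, D.4.i, D.5.iii, D.5.iv).

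| Assumption | Arithmetic | Studies |
|---|---|---|
| All women complete three | 40 × 3 | 120 |
| All complete two | 40 × 2 | 80 |
| 37 complete three, 3 give two each | 111 + 6 | 117 |
| 37 complete three, 3 give one each | 111 + 3 | 114 |
| 37 complete three, 3 give none | 37 × 3 | 111 |
| Each completes the required one | 40 × 1 | 40 |
| 37 complete one, 3 give none | 37 × 1 | 37 |

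The plan's figure is reproduced only by the first row, which leaves no room for the dropouts.

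**2. The plan's 37.** Inputs: late-pregnancy AUC 2.34, SD 1.82 (D.5.xiii), or a late mean of 2.4 (D.6); alpha 0.05, taken as two-sided; power 80% (D.5.xiii labels the 0.80 as beta). For two independent groups, n per group = 2 × (1.960 + 0.842)² × (SD/difference)² = 15.70 × (SD/difference)².

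- Difference 1.20 (50% of 2.4): 15.70 × (1.82/1.20)² = 36.1, rounded up to **37**.
- Difference 1.17 (50% of 2.34): 15.70 × (1.82/1.17)² = 37.98, rounded up to 38, or 39 with the t distribution.

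So 37 is consistent with an unpaired early-versus-late calculation per window. Other combinations of difference, SD and correlation also give values near 37, so the arithmetic does not prove which was used.

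**3. The same contrast, paired.** The SD of the difference is 1.82 × √(2(1 − ρ)), taking the early SD as equal to the late SD. For a difference of 1.17 and 80% power (t-based), at assumed within-woman correlations ρ:

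| ρ | SD of difference | Pairs needed |
|---|---|---|
| 0 | 2.574 | 40 |
| 0.3 | 2.153 | 29 |
| 0.5 | 1.820 | 21 |
| 0.7 | 1.410 | 14 |

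At moderate correlation, 37 pairs would be more than enough and would leave room for missed visits.

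**4. Early pregnancy versus postpartum.** SDs 1.82 (assumed for early pregnancy) and 2.8; root mean square √((1.82² + 2.8²)/2) = 2.361. With 37 women per window, unpaired, the power depends on what the 50% is taken of:

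- 50% of an early mean halfway between 2.34 and 4.0: 0.5 × 3.17 = 1.585, power 81%.
- 50% of the postpartum mean: 2.0, power 95%.
- 50% of 2.34: 1.17, power 56%. This is the extreme case in which the early mean equals the late mean.

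Paired at ρ = 0.5, the SD of the difference is √(1.82² + 2.8² − 2 × 0.5 × 1.82 × 2.8) = 2.461, and the pairs needed are 21, 14 and 37 respectively.

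**5. The SD itself.** D.5.xiii implies coefficients of variation of 1.82/2.34 = 78% and 2.8/4.0 = 70%. D.6 gives 50%. At 50% of 2.34, the SD is 1.17, and 37 per window gives 99% power for early versus late at a difference of 1.17, against 78% with SD 1.82.

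**The case against.** The strongest defence is that 120 is simply the design intention in D.1, three visits by 40 women, and that no power calculation uses it. The physiologic outcomes also rest on the small pupil variance, so the error lies in one sentence and the analyses it supports may still be sound. This stands: the defect is a maximum worded as an expectation.

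The unit of the 37 is also clear to a point. Three subjects are added to it, and D.1 ties the 40 to the PK study. Only the visits a subject must complete are unstated.

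The Secondary Hypotheses text says its paired t-test follows what was described before, and the Data Analysis Plan lists mixed-effect models first. The plan therefore already allows incomplete women to be used. That is true, but the choice among three methods is left open, and the only method named specifically for AUC in pregnancy versus postpartum is the one that drops them.

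A reader might infer that the trial is underpowered. The documents do not support that. They give no within-woman correlation, no early-pregnancy mean or SD and no completion rate. D.7 says only that dropout may be higher than usual, and offers ways to reduce it. The low power of 56% in the working depends on the extreme case, and other plausible inputs give ample power. Nor is the 37 shown to be arithmetically wrong.

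**Conclusion.** The point holds as a matter of justification and definition. The stated 120 is the ceiling. The paragraph's own two to three visits give 80–120, its dropouts hold the total to 111–117 at most, and the one-study rule guarantees only 40 (37 if three women give none). The 111 assumes that dropouts contribute nothing, and the 117 that each contributes two studies.

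The 37 is a number of subjects that an unpaired early-versus-late calculation reproduces, but which visits make a subject count is not stated. Replacement is stated only for dismissed women, so the rules do not secure 37 women in each window or 37 pairs. Whether this costs power cannot be decided from the documents.

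If the paired t-test is used for AUC, single-visit women leave that comparison although the rules admit them. They would still inform the population PK model. The plan should be corrected before analysis, mainly so that the choice of test is not made after the pattern of missed visits is known.

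**What to change.** 1. **D.5.xiii, Primary Hypothesis.** Replace the 120 with: at most 120 studies (40 women × 3 visits); 80–120 if every woman completes two or three; 111 if 37 women complete all three and three give no data; as few as 40 if each woman completes only the required one. Note that studies are clustered within woman.
2. **Meaning of the 37.** State whether it refers to women per window or to women contributing to both windows of a contrast, whichever was used. Give power separately for early versus late pregnancy and for early pregnancy versus postpartum, at the number completed, with the assumed difference, SD (reconciled with the 50% coefficient of variation in D.6) and within-woman correlation. Report the women completed in each window and each pair of windows.
3. **Data Analysis Plan and Secondary Hypotheses.** Make the mixed-effects model, with a random effect for woman and all completed visits, the primary analysis of dose-adjusted AUC. Keep the paired t-test as a completers-only sensitivity analysis. Use a woman-level random effect in the physiologic–concentration analyses too.

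The cost is revised wording and one count table, with no added patients or visits. The sponsor accepts a less favourable study count, a power statement given as a range, the loss of a free choice among three methods, and reliance on a missing-at-random assumption for missed visits. That assumption deserves a sentence of its own, because some visits are missed after a positive drug screen.
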